6.3. Study visits/Follow-up

Two maternal follow-up study visits will be scheduled to ascertain outcomes at the same time as routine clinical visits (~7 days postoperative & ~ 6 weeks postpartum visit). These visits are standard postpartum visits at UTMB. The standard procedure in our postpartum care unit is that the providers will schedule the postpartum visit before the patient leaves the hospital. Our research staff will document the time and dates of the postpartum appointments in the datasheet in order to confirm follow up. The subject will be informed of the appointment and will be given a phone number for any questions and concerns regarding the study (contact information will be in the consents). Subject participation will end after their 6 week post partum visit.

At the visits, the research staff or trained provider will obtain relevant outcomes described in section 6.7. We will also review the electronic medical record for the relevant outcomes. We will have research staff at every obstetrical clinic available during regular hours. If the subject does not present at the visits, or the survey was not completed during the visit, every effort will be made to contact her by phone and outcomes further ascertained. If greater than 30 days have passed from the last scheduled visit and the subject could not be reached, she will be designated as lost to follow-up.

6.4. Baseline Procedures

Routine post-cesarean care will be according to the subjects' clinical providers. Trained and experienced research staff will be responsible for all research data abstraction. The PI will review and validate the data. Data on these forms devoid of personal identifiers will be securely stored in our perinatal research division offices.

6.5. Device Dispensation

Initial receipt of stapler and materials from the sponsor will be kept in a locked research room with limited access. Receipt of the devices will be documented. Once the study is approved; the devices will be maintained in Labor and Delivery in a locked area ready for access after patient is randomized. This is similar to our other L&D studies where materials/devices are needed. Clinical staff will be trained by the sponsor as an inservice and a log will be created to document training before initiation of recruitment.

6.6 Withdrawals

Subjects who withdraw from the study after randomization will be excluded from further follow-up. Outcomes will be reported by intent to treat fashion. Those who withdraw prior to ascertaining of the primary outcome and refuse further data collection will be accounted for by randomizing an equal number of additional subjects and will not be included in the analysis. Patients will be reassured that participation in the study is voluntary and they are able to withdraw at any time if they wish.

6.6. Primary Outcome

OR Case time in minutes

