- Will be undergoing cesarean delivery.

5. Exclusion Criteria:

- Patient unwilling or unable to provide consent.
- No or very limited prenatal care or a non-resident patient who is unlikely to follow-up after delivery.
- Immunosuppressed subjects: i.e., taking systemic immunosuppressant or steroids (e.g. transplant subjects; not including steroids for lung maturity), HIV with CD4 <200, or other.

- Decision not to have skin closure (e.g. secondary wound closure, mesh closure).
- Current skin infection.
- Coagulopathy.
- High likelihood of additional surgical procedure beyond planned cesarean with our without tubal ligation (e.g. scheduled hysterectomy, unplanned tubal ligation, bowel or adnexal surgery).
- Incarcerated individuals.
- Intraamniotic infection.
- Subjects participating on other treatment trials or studies that would interfere with the current study's primary outcome.

6. Study Procedures:

6.1 Screening Recruitment and Consenting:

Under the direction of the PI, trained research staff will be available 24/7 to screen and consent subjects. Subjects will be enrolled at the time of admission to labor and delivery (L&D) for delivery or thereafter when decision for cesarean section is made. Medical records of all potential subjects will be reviewed and those who satisfy eligibility criteria will be approached and written informed consent obtained. Potential subjects with whom there is no treating relationship, the permission of the treating provider will be obtained prior to approaching subjects to participate in the study. A screening log will be used to track all subjects approached for the study. Women will be randomized in the operating room when the decision is made to proceed with skin closure and they continue to be eligible.

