6.2 Randomization

A confidential computer-generated simple randomization scheme will be prepared and provided on an ongoing basis to our research staff. A randomization log with group assignment, patient name and medical record number will be used to track the randomization process.

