Each patient will be assigned a study number with personal identifiable information deleted or removed. Subjects' information will be de-identified and tagged with a number. Data will be collected and stored on a UTMB password-protected computer in a locked room.

The data collected will be kept on a password-secured UTMB computer. An encrypted USB flash drive will be used to transfer data. The data will be linked to the subject by subject's MRN number. This identifier is needed to access and analyze demographic data. During analysis of the data, all identifiers will be deleted.

11. Potential Benefits

A potential benefit is that the novel stapler device leads to shorter operating room time, better aesthetic outcomes, improved patient satisfaction, and less pain. We also hope that this novel stapler will ultimately reduce SSI rates and maternal health costs.

12. Statistical Approach

Analysis will be performed by intent to treat. For this analysis, normality will be tested using Shapiro-Wilk method. Between-group differences in continuous variables will be assessed using Student t test or Man-Whitney rank sum test and results will be given as mean, standard deviation, or median range as appropriate. Categorical variables will be assessed using the Pearson chi-square test or Fisher exact test as appropriate. For dichotomous endpoints, relative risk (RR) and 95% CI values will be calculated. P < 0.05 will be considered significant. The analysis will be performed after study completion.

Sample size was calculated based on the determination of superiority. The primary outcome is operative time in minutes. Based on our institution's usual operating time for a routine cesarean section, the mean of operative time in patients undergoing incision closure with sutures was 55.46 with a standard deviation of 13.63 mins. We estimated that the absorbable staples would lead to a decrease in time by 5 mins. If we calculate the sample size based on 90% power to confirm superiority and an alpha of 0.05, we estimate we would need a total of 316 patients. Assuming a 10% loss to follow-up, we plan to enroll a total sample size of 352 (176/group). STATA 16 (Dallas, TX) will be used for statistical computations. This trial will be registered with Clinical Trials Register (Clinicaltrials.gov), before recruitment is initiated and after IRB approval.

Below is the sample size calculation protocol:

T tests - Means: Difference between two independent means (two groups)

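### Randomization comes at the decision to close skin, but the primary test compares whole case time without adjusting for time already elapsed: valid, but less precise than it need be

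*Combined protocol and SAP*

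**What the plan says.** Section 6.6 (Primary Outcome) consists of one line, "OR Case time in minutes". Section 12 names it differently, "The primary outcome is operative time in minutes", and plans on whole-operation figures from the institution's routine cesareans: "the mean of operative time in patients undergoing incision closure with sutures was 55.46 with a standard deviation of 13.63 mins". Neither section gives a start or stop point.

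Section 6.1 sets the time of randomization: "Women will be randomized in the operating room when the decision is made to proceed with skin closure and they continue to be eligible". Section 6.2 describes what is recorded: "A randomization log with group assignment, patient name and medical record number will be used to track the randomization process". No time is mentioned there. Section 6.5 keeps the staplers "in a locked area ready for access after patient is randomized".

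The analysis in section 12 is unadjusted: "Between-group differences in continuous variables will be assessed using Student t test or Man-Whitney rank sum test". No covariate is named for any outcome.

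**The concern.** Case time is the sum of two parts: the time up to randomization and the time after it. Only the second can respond to the closure method. On any reading of case time that starts before skin closure, the first part is fixed before allocation, and its variation adds only noise to the comparison.

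The question is whether a device saves a few minutes at the end of an operation of about 55 min. Randomization is simple and unstratified (section 6.2), so nothing in the design limits chance differences between arms in elapsed time. The 5 min target is an estimate by the investigators. If the true saving is 3 to 4 min, the unadjusted comparison may miss a difference that the same women could have shown.

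**Working it through.** **Inputs from section 12.** SD 13.63 min; target difference 5 min; two-sided alpha 0.05; power 90%; 1:1 allocation; 316 analysed (158 per arm); 352 enrolled (176 per arm).

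**Input not in the documents.** The residual SD of case time once elapsed time at randomization is known. If the two parts are independent, this equals the SD of post-randomization time. A range of 13 to 4 min is assumed.

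**Step 1: reproduce the plan's figure.** Standardized effect = 5/13.63 = 0.3668. With 158 per arm the noncentrality is 0.3668 × √(158/2) = 3.2605, on 314 df, with critical t 1.9675. Noncentral-t power is 0.9016. This matches the output printed in section 12, and 316/0.90 rounds up to 352.

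**Step 2: precision of the planned test.** SE = SD × √(2/n), and half-width = critical t × SE.
- 176 per arm: SE = 13.63 × √(2/176) = 1.453 and half-width = 1.967 × 1.453 = 2.86 min. Power is 93%, 78% and 54% for savings of 5, 4 and 3 min.
- 158 per arm: half-width 3.02 min. Power is 90%, 74% and 50%.

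The 176 figure is the more relevant one, because the primary outcome is measured in the operating room and later loss to follow-up should hardly touch it.

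**Step 3: the same women, adjusted for elapsed time.** Replace 13.63 by the residual SD and give up one more degree of freedom. Share of information lost without adjustment = 1 − (residual SD/13.63)². All rows are at 176 per arm except the last column.

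| Residual SD (min) | Half-width (min) | Power for 3 min | Saving detectable with 80% power (min) | Information lost unadjusted | Total N for 90% power at 5 min |
|---|---|---|---|---|---|
| 13.63 (unadjusted) | 2.86 | 54% | 4.08 | – | 316 |
| 13 | 2.73 | 58% | 3.89 | 9% | 288 |
| 12 | 2.52 | 65% | 3.59 | 22% | 246 |
| 10 | 2.10 | 80% | 2.99 | 46% | 172 |
| 8 | 1.68 | 94% | 2.40 | 66% | 110 |
| 4 | 0.84 | over 99% | 1.20 | 91% | 30 |

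Half the information is lost when the residual SD is 13.63/√2 = 9.64 min.

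**Step 4: chance imbalance.** With a post-randomization SD of 8 min and independent parts, the SD of elapsed time is √(13.63² − 8²) = 11.04 min. The arms' mean elapsed times then differ by chance with SE 11.04 × √(2/176) = 1.18 min, a 95% range of about ±2.3 min. That is nearly half the 5 min target.

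**Step 5: validity.** In simulations at 176 per arm (4,000 runs per setting) the false-positive rate was 4.8–5.0% unadjusted and 4.5–5.2% adjusted. Power for 3 min was 53–54% unadjusted and 63%, 81%, 94% and 100% adjusted at post-randomization SD 12, 10, 8 and 4. Both tests are valid.

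**Step 6: which time to adjust for.** Staplers are fetched after randomization, so the start of skin closure may itself differ by arm. Simulation (3,000 runs, post-randomization SD 8) assumed a closure saving of 3 min and a retrieval delay of 1 or 2 min, so that the true net saving was 2 or 1 min. Adjusting for start of closure gave 3.0 min in both cases. Adjusting for time of randomization gave 2.0 and 1.0 min.

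**The case against.** The strongest reply is that the plan meets its own objective. The test is unbiased, the sample size is right, and at 352 women power for 5 min is 93%. The 3 to 4 min range is not the sponsor's. All this stands; the point is an improvement to a working design and does not show that the trial would fail.

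Second, the size of the gain is unknown. This also stands. At a residual SD of 13 min, adjustment moves power for 3 min only from 54% to 58%. The large gains need most of the variation to arise before closure, which is plausible when randomization comes at the last step but is not shown.

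Third, OR case time and operative time may be different intervals, in which case 13.63 is not the SD of the named outcome. Section 12 treats them as one, so the figures follow the plan; if they differ, every half-width scales with the SD. Variable time after closure, such as the wait until the woman leaves the room, would also weaken the covariate. This is why the definition must come first.

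Fourth, the log may hold more than section 6.2 lists, and no concealment mechanism is described there. The first part makes the missing time field an inference from silence. The second matters for the fix, which needs a time entered before the assignment is known.

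None of these removes the case for adjusting. It costs one degree of freedom, and the documents do not show that the time could be recovered afterwards.

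**Conclusion.** The concern holds as a loss of efficiency, not as bias or a wrong sample size. As planned, the saving will be estimated to within ±2.86 min with 176 per arm, and a true saving of 3 min has 54% power. Adjustment would narrow this to ±2.52, ±2.10 or ±1.68 min if the residual SD is 12, 10 or 8 min, and less if it is nearer 13.63. More than half the information is discarded only if that SD is below 9.64 min.

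The figures rest on 13.63 min being the SD of the primary outcome, on an assumed range for the residual SD, and on sound randomization. The change should be made because it is cheap, acts on the primary estimate and must be in place before recruitment. Confidence in the size of the gain is only medium.

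**What to change.** 1. In section 6.6 (Primary Outcome), keep OR case time, state its start and stop points, and use the same term in section 12.
2. Add a clock-time field to the randomization log in section 6.2, completed before the assignment is revealed and before any arm-specific device is fetched.
3. In section 12, prespecify a linear regression of case time on arm with time from case start to randomization as covariate. Report the adjusted mean difference with its 95% CI as the primary result, and keep the unadjusted comparison as a sensitivity analysis.
4. Do not use start of skin closure as the covariate.
5. Skin-closure time may be added as a secondary outcome. It should not replace case time: it would leave out any device-handling delay, and the aim in section 1 is operative time.

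The cost is one log field and about one sentence in each of the sections named, with no extra patients. The documents do not say who in the operating room would record the time, so that task has to be assigned and the moment of the decision to close has to be defined well enough to be timed.

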6.7. Secondary Outcomes

- Need of in hospital analgesics
- Composite wound complication.
 - Defined as presence of any of the following within 30 days from surgery: Wound infection: Presence of either superficial or deep incisional surgical site infections described as cellulitis/erythema and induration around the incision or purulent discharge from the incision site, with or without fever, such as necrotizing fasciitis (diagnosed based on necrotizing wound infection). Wound hematoma, seroma, or breakdown alone.

- Endometritis, wound infection (including necrotizing fasciitis), other infections including abscess, septic thrombosis, pneumonia, pyelonephritis and breast infection.
- Maternal Death.
- Puerperal fever: temperature >100.4°F after first 24 hours or ≥101°F any time.
- Postpartum antibiotic use.
- Wound hematoma or seroma.
- Wound dehiscence.
- Use of resources: hospital stay, postpartum clinic or emergency room visit within 30 days of delivery, need for imaging or other invasive procedures.
- Adverse events: allergic reactions (anaphylaxis, angioedema, skin rashes including Stevens Johnson and Toxic Epidermal Necrolysis).
- Bluebelle Wound Healing Questionnaire for assessment of surgical-site infection/wound complications in closed primary wounds during wound check visit on POD 5-10 days standard visit, which will be completed by the patient
- Analog pain scale ranging from 0-10 on postoperative days 1 to 3 as well as at wound check visit, this is a standard question that nurses as during the post partum period while in the hospital and clinic/nursing visits. The numerical score will be recorded from the patient's chart.
- Wound cosmesis on POD 5-10 visit postpartum visits: A digital photograph of the incision will be obtained on wound check visit POD 5-10 days and 4-6 weeks postoperative. Each photograph will be evaluated according to objective criteria (width, elevation, color, marks, and general appearance) by independent blinded research staff using the Stony Brook Scar Evaluation Scale
- Satisfaction a questionnaire POD 2-3 (before discharge) and at wound check visit (Appendix B).

7. Sources of Research Material:

Electronic Medical chart/records, questionnaires, photographs.

8. Potential Risks:

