8.1. Study Risks

Adverse effects (rare events overall <2%) include irritation, redness, itchiness, discomfort, infection, and allergic reaction. Subjects will be closely monitored for all side effects. For side effects/adverse events, patients will be treated with standard medical care to address their symptoms. The arm that they are enrolled in will not influence treatment.

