8.3. Loss of Confidentiality

Any time information is collected there is a potential risk for loss of confidentiality. Every effort will be made to keep patient's information confidential; however, this cannot be guaranteed.

9. Subject Safety and Data Monitoring

The PI and research staff will be responsible for monitoring the safety of this study. A report to the IRB will be submitted according to its policy if adverse events (AEs) or serious adverse events (SAEs) occur, and any changes in the protocol as a result of these events. No interim analysis will be planned and there will be no study-specific criteria to halt the study. Since, Monocryl and INSORB absorbable stables are deemed safe and available for use according to the FDA, there are no safety and minimal toxicity concern.

The research staff will ensure all aspects of data quality including monitoring for adherence to consent procedures, inclusion and exclusion criteria, valid abstraction, correct entry, timeliness and responsiveness to data queries.

Data collection will take the form of excel data entry and will be identified with a participant ID number. Data will be collected and stored with the participant ID code only. The master enrollment log linking patient identifiers with study ID numbers will be kept in a password-protected database on the Ob/Gyn Department's internal server separate from the data. Several data collection forms will be used. Data on these forms devoid of personal identifiers will be securely stored at our perinatal research division. The research staff will be available to monitor the data and correct any discrepancies based on source documents if needed. The principal investigator and research staff will monitor the study accrual rate, study attrition including withdrawals/dropouts, and any changes in risk/benefit bi-annually.

Each subject will be provided contact information to reach study staff. Additionally, the consent form provides instructions and a mechanism of contact for subjects to reach the primary investigator and also provides contact information for the subject to contact the IRB directly. Any significant concerns or complaints or requests for study information would be directed from the study staff to the study coordinator and study PI. Any complaints or adverse events gleaned from these contacts would be reported to the IRB (per IRB policy) and to the sponsor.

10. Procedures to Maintain Confidentiality

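### The adverse-event outcome covers allergic reactions only, so irritation, itchiness and non-infectious redness, which section 8.1 names, have no stated count by arm

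*Combined protocol and SAP*

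**What the plan says.** Section 6.7 has one item headed as adverse events, and it is confined to allergy: "Adverse events: allergic reactions (anaphylaxis, angioedema, skin rashes including Stevens Johnson and Toxic Epidermal Necrolysis").

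Section 8.1 lists more: "Adverse effects (rare events overall <2%) include irritation, redness, itchiness, discomfort, infection, and allergic reaction". It adds: "Subjects will be closely monitored for all side effects".

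On collection, section 6.3 states that at the two follow-up visits "the research staff or trained provider will obtain relevant outcomes described in section 6.7", with review of the medical record for the same outcomes.

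Three other section 6.7 items bear on the section 8.1 list:
- Wound infection includes "superficial or deep incisional surgical site infections described as cellulitis/erythema and induration around the incision".
- Pain is the "Analog pain scale ranging from 0-10 on postoperative days 1 to 3 as well as at wound check visit".
- Cosmesis is scored from photographs by blinded staff: "Each photograph will be evaluated according to objective criteria (width, elevation, color, marks, and general appearance").

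Section 9 sends adverse events to the IRB under IRB policy and says that the investigator and research staff "will monitor the study accrual rate, study attrition including withdrawals/dropouts, and any changes in risk/benefit bi-annually". Section 12 specifies relative risk with 95% CI for dichotomous endpoints and has no separate adverse-event analysis.

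**The concern.** The plan names its expected adverse effects in one section and defines a narrower adverse-event outcome in another. Because section 6.3 ties visit collection to the narrower list, a woman whose incision is itchy and irritated, without infection or allergy, meets no stated outcome definition. A results table headed adverse events could then show no difference between closures without having counted the mild local effects that the plan lists.

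Redness needs particular care. The Background (section 2) warns that staple closure can be mistaken for wound infection because it comes with induration and erythema. That remark follows a discussion of steel staples, but the infection definition in section 6.7 relies on the same signs. With no category for redness without infection, a reactive incision is either classed as infection, which adds to the wound composite, or is not classed at all.

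**Working it through.** **Coverage.** Each effect in section 8.1 set against the section 6.7 outcomes:

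| Section 8.1 effect | Matching section 6.7 outcome |
|---|---|
| Allergic reaction | Adverse-event item |
| Infection | Wound-infection and other infection items |
| Discomfort | 0–10 pain scale, days 1–3 and wound check |
| Redness | By name (erythema) only within wound infection; scar colour is part of a cosmesis score |
| Irritation | None stated |
| Itchiness | None stated |

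Three of the six are fully matched, redness is matched only as infection, and two are unmatched. The general monitoring statements in sections 8.1 and 9 give no event definition, form, time window or tabulation by arm.

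**The plan's sample size, to confirm that the fix leaves it alone.** Inputs from section 12: difference 5 min, SD 13.63, two-sided alpha 0.05, power 90%, 1:1 allocation.
- d = 5 / 13.63 = 0.3668.
- The t-test solution is 157.13 per arm, rounded up to 158 (316 in total), with power 0.9016. This matches the plan.
- 316 / (1 − 0.10) = 351.1, rounded up to 352, or 176 per arm. This also matches.

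None of these inputs involves adverse events.

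**What the added items could show.** The only rate in the documents is the under-2% figure in section 8.1, read here as a ceiling for all six effects together and applied to each arm.
- Expected events: 0.02 × 176 = 3.52 per arm, 7.04 in total.
- Chance of at least one event in an arm: 1 − 0.98^176 = 0.97.

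The documents give no rate by arm, so the second rate in each pair below is an assumption. The normal approximation is power = Φ[(|p2 − p1| − 1.96·SE0) / SE1], where SE0 uses the pooled proportion and SE1 the separate proportions, with 176 per arm.

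| Rates compared | Normal approximation | Fisher exact |
|---|---|---|
| 2% v 4% | 19% | 11% |
| 2% v 6% | 48% | 38% |
| 2% v 8% | 73% | 68% |

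Worked for 2% v 6%: SE0 = √(2 × 0.04 × 0.96 / 176) = 0.02089 and SE1 = √((0.0196 + 0.0564) / 176) = 0.02078. Then (0.04 − 0.04094) / 0.02078 = −0.045, and Φ = 0.48. Reaching 80% power for this pair would need 376 per arm. The comparison is therefore descriptive at the planned size.

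**The case against.** The strongest reply is that an event missing from one secondary-outcome line is not missing from the trial. Section 8.1 promises surveillance of all side effects, section 9 routes adverse events and complaints to the IRB, and the medical record is a data source. There is also partial overlap. Skin rashes in the adverse-event item are not limited to the two severe forms named, so an itchy local rash judged allergic would count. Scar colour is scored blind in both arms. The patient-completed wound questionnaire and the satisfaction questionnaire (Appendix B) may ask about these symptoms, but their items are not printed.

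This limits how far the point can be taken. Five stronger readings are tempting, and the documents do not support them:
- That these are risks of the stapler. Section 8.1 is headed as study risks and assigns them to neither closure.
- That the arms cannot be compared on them. Some data may exist in charts or questionnaires; what is missing is a stated outcome with uniform collection.
- That the adverse-event count must be close to zero by definition. Non-severe allergic rash is eligible, and no rate for allergy alone is given.
- That the twice-yearly review would see only the section 6.7 items. Section 9 does not restrict it in that way.
- That a known number of women would go uncounted. An assumed 5–10% rate would give about 9 to 18 of 176, but no such rate appears in the documents.

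What does not fall is the mismatch. None of the overlapping sources is a stated count by arm of irritation, itchiness or redness without infection. Unprompted charting in an open-label trial may also be uneven between arms.

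**Conclusion.** The point holds as a mismatch between sections 6.7 and 8.1. Followed as written, the plan gives an adverse-event comparison that leaves out irritation, itchiness and redness without infection, although it names all three effects and says that all side effects are monitored. It should be corrected, but its reach is limited to secondary safety reporting.

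In size, the gap covers two named effects entirely and a third in its non-infectious form. At the 2% ceiling, no more than about 3.5 events per arm are expected across all six effects, so the gain is complete and consistent reporting, not a powered test. This rests on two assumptions: that the under-2% figure covers all six effects together and applies to both arms, and that the unprinted questionnaires do not already supply these counts. If they do, the plan need only name them as the source for the visits they cover.

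**What to change.** 1. Reword the adverse-event item in section 6.7 to cover every effect in section 8.1, with allergic reactions kept as a sub-item.
2. Record irritation, itchiness and redness without infection as yes/no with date, using identical questions in both arms at the POD 5–10 and 6-week visits.
3. In section 12, report counts by arm with relative risk and 95% CI, as already specified for dichotomous endpoints, and label the comparison descriptive.
4. Use the same table by arm in the twice-yearly review under section 9.

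The cost is protocol wording and a short checklist at two existing visits, with no change to the sample size. There are three downsides. The reported adverse-event rate will be higher than under the present definition. Answers on itch and irritation are subjective and may be coloured by knowledge of the closure; identical questions lessen uneven ascertainment but do not remove this. Precision will be low at the expected event numbers, so an interval that includes no difference should not be read as evidence of equal safety.

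### POD 3 pain is likely to be compared only among women still in hospital, and section 12 has no method for scores missing because of discharge

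*Combined protocol and SAP*

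**What the plan says.** Section 6.7 (Secondary Outcomes) sets an "Analog pain scale ranging from 0-10 on postoperative days 1 to 3 as well as at wound check visit". It describes the score as routine: "this is a standard question that nurses as during the post partum period while in the hospital and clinic/nursing visits". It adds that "The numerical score will be recorded from the patient's chart".

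The same section lists "Satisfaction a questionnaire POD 2-3 (before discharge) and at wound check visit", and it also makes length of stay an outcome: "Use of resources: hospital stay".

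Section 12 (Statistical Approach) promises an intention-to-treat analysis and states that "Between-group differences in continuous variables will be assessed using Student t test or Man-Whitney rank sum test". It names no repeated-measures method, no main pain day or summary, and no rule for a score that is missing because the woman has gone home. The telephone contact in section 6.3 covers missed visits and surveys not completed at a visit. It does not cover daily pain after discharge.

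**The concern.** A chart score taken by ward or clinic nurses exists for POD 3 only if the woman is still there when it is taken. If discharge begins within the POD 1-3 window, a two-sample test on POD 3 uses whoever remains. That group is formed after randomization, and its make-up may depend on pain and possibly on arm, since the trial is open-label (section 3) and staff know which closure was used.

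Two things are at stake. The POD 3 comparison loses precision with every early discharge. It can also mislead: if staple women go home sooner and those in less pain leave first, the remaining staple women have more pain than the arm as a whole. That could create a false difference against staples or hide a real benefit. Section 11 names less pain as a potential benefit of the device, so the pain results are likely to be read closely.

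**Working it through.** **1. The plan's own figure.** The only sample-size calculation is for operative time. d = 5/13.63 = 0.3668. With 158 per arm, the noncentrality is 0.3668 × √(158/2) = 3.2605 and power is 0.9016, so 316 reproduces. Allowing for 10% loss, 316/0.9 = 351.1, rounded up to 352. None of this is affected. The documents give no SD, expected difference or discharge distribution for pain, so every pain figure below rests on stated assumptions.

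**2. Precision.** With n women per arm scored, the difference detectable with 90% power at two-sided 0.05 is (1.960 + 1.282) × √(2/n) SD. Starting from 158 per arm:

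| Share still in hospital on POD 3 (assumed) | n per arm | Detectable difference |
|---|---|---|
| 100% | 158 | 0.365 SD |
| 75% | about 118 | 0.42 SD |
| 50% | 79 | 0.52 SD |
| 25% | about 40 | 0.73 SD |

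**3. Bias in closed form.** Suppose pain (in SD units) and a tendency to stay are bivariate normal with correlation ρ, and a share p of an arm remains. Mean pain among those remaining is ρ × φ(z)/p, where z cuts off the upper share p. The factor φ(z)/p is 0.399/0.5 = 0.798 at p = 50%, 0.386/0.4 = 0.966 at 40%, and 0.348/0.3 = 1.159 at 30%. With no true effect, the apparent excess pain in the staple arm is:

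- 50% suture and 50% staple remaining: ρ × 0 = 0, whatever ρ is.
- 50% and 40%: ρ × 0.168, that is 0.05 SD at ρ = 0.3 and 0.08 SD at ρ = 0.5.
- 50% and 30%: ρ × 0.361, that is 0.11 SD and 0.18 SD.

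If ρ = 0 the bias is zero however unequal the shares. Simulation with 158 per arm (20,000 runs) gave type I error of about 6% and 8% at 50% and 40%, and about 10% and 19% at 50% and 30%.

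**4. The same check in points, with a different mechanism.** Assumptions: 176 per arm, pain SD 2, between-day correlation 0.6, log-odds of discharge before the POD 3 score falling by 0.5 per point of POD 2 pain, and no true effect. Ranges cover repeated simulation runs.

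| Discharged, suture v staple | Bias against staples, t test | Type I error, t test |
|---|---|---|
| 40% v 40% | 0.00 | 4.8-5.7% |
| 37.5% v 42.5% | 0.04-0.05 | 5.2-5.4% |
| 35% v 45% | 0.09-0.10 | 6.4-6.7% |
| 30% v 50% | 0.19 | 10.8-11.7% |
| 30% v 50%, slope 0.3 | 0.13 | 7.0-7.6% |

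**5. Gain from a likelihood-based estimate.** An estimate using all POD 1-3 scores had bias within 0.01 points and type I error of about 5% in these settings. With equal 50% discharge and a true 0.6-point difference, power was 79% with complete data, 53% for the restricted t test and about 61-62% for the likelihood estimate. With a true 0.6-point staple benefit and about 30% v 50% discharged, the t test estimated 0.35 points (power 23%) and the likelihood estimate 0.60 points (power 57%).

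**The case against.** The strongest reply is that the gap is inferred. A reader might conclude that the protocol says women are discharged on POD 2-3. It does not: it only times a questionnaire before discharge, and that also fits discharge on POD 3 or later. A woman who leaves on POD 3 may still have a charted score for that day. This stands; the share affected is unknown and could be small.

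A reader might also infer that the POD 3 comparison is biased. The documents do not show this. Bias needs both arm and pain to relate to discharge timing. Section 3 says other care will be similar in the two arms, and nothing gives an arm effect on stay. A 5-point difference in discharge barely moves the error rate. This stands too, although knowledge of the arm keeps an effect on discharge possible, and the precision loss needs no such effect.

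Testing each day separately is the natural reading of section 12, not a stated rule. A per-woman mean or worst score is not excluded, but it would meet the same gap and would also need a missing-data rule.

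It is tempting to extend the point to cosmesis and satisfaction because each is measured twice. The mechanism does not carry over. Photographs are taken at visits after discharge, the first satisfaction questionnaire is completed before it, and section 6.3 provides telephone follow-up for surveys not completed at a visit. With complete scores, the mixed model proposed here gives the same per-visit differences as two-sample comparisons.

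Finally, the model recovers only part of the lost power, since most of the fall comes from data that do not exist.

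**Conclusion.** The point holds in a limited form. The plan collects POD 3 pain by a route that stops at discharge and gives only two-sample tests for it. On the natural reading, it would compare a subset formed after randomization under an intention-to-treat heading. Some precision is lost if any women leave before that score. Bias is a risk and not a finding: zero with equal discharge and equal selection, about 0.09 points at 35% v 45% discharged and about 0.19 points at 30% v 50%, with type I error of about 6% and 11%. These sizes rest on the assumed SD, correlation, slope and discharge shares, none of which the documents supply.

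Pain is one of many secondary outcomes. The primary outcome and its sample size are untouched. POD 1 and wound-check pain do not depend on being in hospital on POD 3, but nothing in the documents ranks POD 1 above the other times, so no main pain day follows from this point.

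**What to change.** In section 12, state that pain will be analysed with one likelihood-based mixed model for repeated measures: arm, day and arm-by-day terms, unstructured covariance, and all observed scores from POD 1 to 3 and the wound check. Report the between-arm difference for each day with its 95% CI, and the number of women with a score by arm and day, so that readers can see how far discharge has thinned each comparison.

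The cost is one paragraph and a routine model in the planned software, with no new data. The downside is a missing-at-random assumption: given arm and the recorded scores, discharge must not depend further on the unrecorded pain. That is weaker than the assumption the restricted test needs, namely that discharge is unrelated to pain within each arm or selects women identically in both. If discharge depends on pain that was never recorded, some bias remains, and the counts by arm and day show how much could be at issue.
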